## **HUMAN SUBJECTS**

All studies in volunteers will be performed in the CRU, which includes monitoring and resuscitation equipment and trained nursing support staff, or in in-patient settings of the Wake Forest Baptist Medical Center. All studies will be approved by the IRB and written informed consent obtained. The Project Investigators have all performed similar studies in volunteers and patients. The purpose of the study and all risks will be discussed with each volunteer, and all questions will be answered prior to obtaining written informed consent. Risks to be discussed include discomfort with needle and catheter insertion, risk of postdural puncture headache and spinal needle insertion, and potential period of pain if the study drugs are ineffective. The most likely bothersome risk to volunteers will be that of headache from i.t. needle insertion. We will discuss options for headache treatment including oral caffeine and epidural blood patch at the time of original consent and again should a headache occur. These will be provided at no charge to the volunteer, paid for by departmental funds. All data acquired will remain confidential with no reference to individuals in publications.

### **Previous Experience in the CRU**

These investigators have, under NIH grant GM48085, regularly performed intrathecal injection studies with novel drugs for intrathecal delivery in healthy volunteers and in patients since 1990. Drugs studied include clonidine, fentanyl, neostigmine, adenosine, ketorolac and oxytocin. In addition, we have studied drugs approved for intrathecal delivery (morphine and bupivacaine) in the CRU. The most common adverse effect from these studies has been mild, transient backache and headache. Persistent headache requiring blood patch has occurred in <1% of subjects, likely reflecting the use of very small gauge (#27), pencil point spinal needles. Drug related adverse effects have included hypotension and bradycardia (clonidine), nausea (fentanyl, neostigmine), mild respiratory depression (fentanyl), transient back and leg pain (adenosine) and one episode of hypotension and bradycardia consistent with a vaso-vagal response to injection (oxytocin). The IRB and FDA recognizes that there are potential risks to these studies and has supported performance of this research in the CRU with the presence of an anesthesiologist and nurse,

appropriate monitoring, intravenous access, and immediate access to appropriate drugs for treatment.

### **Data Safety Monitoring Plan**

This Phase II trial will be performed with a data safety monitoring committee ([name] and [name].) who is not involved in the study. Data and adverse events will be reported to these individuals quarterly. Adverse events will also be reported to the IRB and the FDA (since trials are being conducted under an IND). Serious adverse events will be reported to all of these groups and the data safety monitoring individuals within 24 hr and the trials halted until feedback is obtained from each. Data and any adverse events will be monitored and reviewed by the PI after treatment of each subject.

### **Minority, Gender, and Children Participation**

Based on previous experience with volunteer studies, women will represent 40-60% of participants in the proposed studies. Children under age 18 are not included in these protocols because this protocol involves the use of experimental compounds and we believe they should be first characterized in adults. Furthermore, the study of experimental pain in children volunteers is difficult ethically. For these reasons we anticipate studying approximately 6-7% of our subjects under age 21, and none under age 18.

### **Subject Payment**

Participants will be paid a total of \$800 according to the following payment schedule which we have used throughout the last 2 cycles of this grant's protocols. We believe that this payment schedule is fair and appropriate, paying for each procedure attempted and an additional payment for completion of the entire study.

Placement of IV on each study day: \$25

If IV placement unsuccessful, the volunteer is paid and the study abandoned.

Placement of Spinal on each study day: \$100 and study drug administration

If the 1st spinal is attempted but proves unsuccessful, the volunteer is paid \$100 and the study abandoned.

- Completion of study Visit 2 (first spinal injection): \$150

- Completion of study Visit 4: (second spinal injection): \$250
- Completion of entire study (completion of all study related procedures):  
\$150

Volunteer must complete all of the above phases to receive the total payment.

### **Long-term Follow-up**

Subjects will be contacted daily for 5 days, weekly for 1 month, and at 6 months after the study and questioned about neurologic symptoms, symptoms of post-dural puncture headache (spinal headache) or other complaints. We will also collect a verbal pain score during these follow ups.

### **STATISTICAL RATIONALE**

**Primary outcome measure** will be ongoing pain by visual analog scale.

**Group comparison:** Pain will be compared using a repeated measures ANCOVA.

**Power analysis:** Based on previously published work by us with this model in which the patient population has an ongoing pain level of  $4.3 \pm 2.0$  and a reduction in pain 60 min after injection of  $0.9 \pm 1.5$ , a group size of 40 will allow us to observe a difference between placebo and treatment of 0.7 with  $\alpha=0.05$  and  $1-\beta=0.80$ .

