We subsequently performed several studies which suggest that spinal release of oxytocin represents the protective factor against chronic pain after childbirth. Intrathecal injection of the specific oxytocin receptor antagonist, atosiban, temporarily reverses the blockade of nerve injury induced hypersensitivity in the postpartum period in rats. Similarly, intracerebroventricular administration of the  $\alpha$ -adrenoceptor antagonist, phentolamine, which is known to block the effects of lactation on activation of oxytocin-containing neurons in the paraventricular nucleus (PVN) of the hypothalamus, also temporarily reverses the blockade of nerve injury induced hypersensitivity in the postpartum period in rats. Finally, protection against hypersensitivity from nerve injury is abruptly reversed when pups are separated from dams for 24 hr, and this is accompanied by a large decrease in oxytocin concentration in cerebrospinal fluid. Although we are currently performing more clinical and laboratory studies to further define this mechanism, these data suggest that spinal oxytocin receptor stimulation in the period immediately following delivery protects against the generation of injury-induced hypersensitivity and subsequent chronic pain.

We recently completed a Phase 1 safety study of intrathecal oxytocin and observed no serious adverse events over the dose range studied (5-150  $\mu$ g). One subject at the 150  $\mu$ g dose had transient subjective numbness in sacral dermatomes, but this was preceded by a vasovagal episode beginning just prior to spinal injection, and this did not occur in other subjects at this dose. There were no objective signs of motor or sensory dysfunction in any volunteer, and blood pressure, heart rate, sensorium, corrected QT interval and serum sodium were unaffected.

We anticipate that oxytocin will be effective after spinal injection in humans to acutely relieve chronic neuropathic pain. For these future studies, we will use a cross over, controlled and blinded study of intrathecal oxytocin in patients with neuropathic pain below the umbilicus, with primary outcome being visual analog score for pain and secondary outcomes being areas of increased pain sensation to a normally painful stimulus (hyperalgesia) and pain sensation to what previously was an innocuous stimulus (allodynia).

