## Protocol

### **Efficacy of Intrathecal Oxytocin in Patients with Neuropathic Pain**

**GOAL:** Determine the effect of intrathecal oxytocin on pain and areas and intensity of hyperalgesia and allodynia in patients with chronic neuropathic pain.

**METHODS:** Equal numbers of healthy men and women will be recruited. On a day at least 3 days before study, patients will come to the CTSI Clinical Research Unit (CRU) to review the informed consent, confirm eligibility criteria, and be trained to rate pain in response to heat applied to an area of normal skin without ongoing pain using a Peltier controlled thermode, and to rate pain in response to 225 mN von Frey filament testing within the area of hyperalgesia, if present.

Subjects will come to the CTSI CRU at least 3 days later and be randomized into one of 2 groups of 20 subjects each to receive, in a double-blind manner, intrathecal saline or intrathecal oxytocin, 100 µg. The solutions will be prepared and dispensed to this institution under IND approval and regulation from the Food and Drug Administration and will be released to the investigators through the research pharmacy at Wake Forest School of Medicine. Following subject rating of their ongoing pain and mapping of areas of allodynia and hyperalgesia, as well as rating of pain by a 225 mN von Frey filament applied in the area of hyperalgesia, an intrathecal injection of the study solution in a 3 ml volume will be performed via a #27 or #25 Whitacre needle inserted in a lower lumbar interspace. Subjects will rate their ongoing pain and that from the von Frey filament in the area of hyperalgesia, and we will map the areas of hyperalgesia and allodynia at 30, 60, 90, 120, 180, and 240 min after injection. Subjects will return a second time to the CTSI CRU at least 1 week after the first study session and the same procedures will be performed, except that they will receive the other intrathecal study drug solution (e.g., if they received saline on study session 1, they will receive oxytocin on study session 2).

We will abandon an individual participant's study and schedule another participant to receive the same randomization, should we be unable to successfully place the spinal needle to inject study solution. In our experience, this occurs in less than 10% of participants. Subjects will be recruited at Wake Forest School of Medicine pain clinics, and Orthopaedic and Podiatry

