### **Study Visit 2**

On the second visit, the participant will report to the CTSI CRU in the morning. A peripheral intravenous catheter will be inserted into a vein in an upper extremity and lactated Ringers solution infused at 1.5 ml/kg/hr for the duration of the study. After obtaining baseline measures the subject will be placed into a lateral position and one of the investigator physicians will insert a #25 or #27 Whitacre spinal needle in a lumbar interspace using a sterile technique. After obtaining clear, free-flow CSF, a 2 milliliter sample of CSF will be obtained and stored for future use under IRB Protocol: 00003383, the sample will be stored with a unique identifier.

Oxytocin, 100 µg in a 3 ml volume, diluted with sterile normal saline, or a 3 ml injection of sterile normal saline (placebo) will then be injected over 30 seconds. Oxytocin will be prepared by Med Solutions Compounding, Winston-Salem, NC for research study purposes only. The spinal needle will be removed and the volunteer placed supine with the head of the bed elevated for the next portion of the study. Ongoing pain, pain to 225 mN von Frey filament application in the area of hyperalgesia, and areas of hyperalgesia and allodynia will be determined at 30, 60, 90, 120, 180, and 240 min after spinal injection. Blood samples (5 ml) will be obtained at 10, 20, 40, and 75 min after spinal injection by aspiration from the indwelling catheter, plasma will be prepared from the samples and frozen for subsequent analysis for oxytocin content. If blood cannot be obtained from the catheter we will not collect samples.

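### Does the repeated measures ANCOVA need a named primary time or summary before the trial's result can be trusted?

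*Combined protocol and SAP*

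**What the plan says.** In the Statistical Rationale section the primary outcome "will be ongoing pain by visual analog scale", with no time attached. The Background section describes the design in the same way, "with primary outcome being visual analog score for pain". The line labelled Group comparison reads "Pain will be compared using a repeated measures ANCOVA" and names no tested effect, covariate or analysis times.

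The rating times appear elsewhere. The Methods text of the protocol has ongoing pain rated "at 30, 60, 90, 120, 180, and 240 min after injection", and the Study Visit 2 section repeats the schedule: the measures "will be determined at 30, 60, 90, 120, 180, and 240 min after spinal injection". A pre-injection rating exists for each session: "After obtaining baseline measures the subject will be placed into a lateral position", and Study Visit 4 repeats the procedures of Study Visit 2. Each patient receives both solutions in random order.

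The power analysis draws on published data with "a reduction in pain 60 min after injection" of 0.9 ± 1.5, and concludes that "a group size of 40 will allow us to observe a difference between placebo and treatment of 0.7" at alpha 0.05 and 80% power. The 60 min describes those earlier data. The 0.7 itself carries no time.

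**The concern.** A repeated measures ANCOVA is a family of models, not one test. With six ratings per session it can yield an average treatment effect, a treatment-by-time test and six single-time contrasts. The only time in the statistical section is the 60 min behind the sample size, so two careful readers could defend different primary results. The plan also gives no multiplicity rule.

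If the contrast were chosen after unblinding, the nominal 5% would not hold, and the documents alone would not show whether the reported contrast had been planned. The stated 80% power would also be unclear, because an SD taken at 60 min need not apply to an average over four hours. The Background section reports durations of analgesia from under 1 hr to over 5 hr depending on dose, so the time profile could affect the result.

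**Working it through.** **Inputs.** From the Statistical Rationale: n = 40, SD 1.5, difference 0.7, alpha 0.05 (taken as two-sided), power 0.80. From Methods and Study Visit 2: six ratings. Assumed, because the documents do not give it: the correlation r between a patient's oxytocin-minus-saline differences at different times.

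**The plan's own figure.** Take 1.5 as the SD of the within-patient treatment difference. The standard error is 1.5/√40 = 0.237. The detectable difference is (1.960 + 0.842) × 0.237 = 0.66 by the normal formula and 0.68 by the noncentral t, which round to the stated 0.7. Power for 0.7 is 82% (t). An independent-groups calculation does not reproduce it: 73 per arm would be needed. The sizing is therefore a paired calculation at a single time.

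**Type I error with one contrast fixed.** In 40,000 null trials per setting, with r from 0 to 0.95 and with correlations decaying over time, the 60-min test rejected in 4.7-5.2% and the mean-of-six test in 4.8-5.3%. Both are 5% within simulation error.

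**Type I error if the contrast is chosen afterwards** (two-sided):

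| Choice made after seeing the data | r = 0.3 | r = 0.5 | r = 0.8 | r = 0.9 | r = 0.95 |
|---|---|---|---|---|---|
| Best of six times | 24% | 21% | 14% | 11% | 9% |
| 60 min or average | – | 8% | 7% | 6% | – |

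- Six independent tests give the upper bound, 1 − 0.95⁶ = 26.5%.
- Average or treatment-by-time gives about 1 − 0.95² = 9.75%, and simulation gave about 10%.
- Counting only results that favour oxytocin, best of six runs from about 5% (r = 0.95) to 12% (r = 0.3), against 2.5%.
- With no true effect, the most favourable of six estimates averages 0.21 / 0.13 / 0.10 at r = 0.5 / 0.8 / 0.9.
- The figures above use paired t tests. A smaller check with session baseline and period in the model, under assumed variance components, gave 4.6-5.5% for a fixed contrast, 6.9-8.6% for 60 min or average, and 15.0-23.5% for best of six.

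**Power for 0.7.** The SD of the average is 1.5 × √((1 + 5r)/6) = 1.146 / 1.369 / 1.436 at r = 0.5 / 0.8 / 0.9. Three assumed profiles over the six times:

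- *Constant:* 0.7 throughout.
- *Fading:* 0.70, 0.70, 0.58, 0.47, 0.23, 0; mean 2.68/6 = 0.447.
- *Slow onset:* 0.18, 0.35, 0.52, 0.70, 0.70, 0.70; mean 3.15/6 = 0.525.

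| Profile | 60 min | Average, r = 0.5 / 0.8 / 0.9 |
|---|---|---|
| Constant | 82% | 97 / 88 / 85% |
| Fading to zero at 240 min | 82% | 67 / 52 / 48% |
| Slow onset | 30% | 81 / 66 / 62% |

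The average loses 15 to 34 points if the effect fades, and 60 min loses 32 to 51 points if onset is slow. Neither is better throughout.

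**The case for a change.** The strongest case for acting is that the gap concerns the one result on which the trial is judged. The statistical section is complete as printed, so nothing has been lost to redaction. The analysis sentence suggests all ratings while the sizing suggests 60 min. A sentence naming the effect would cost almost nothing, because every score is already scheduled. Nobody need intend to pick the best time for the choice to drift once the data are known.

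Part of this stands. The deciding effect is not named, and the documents alone do not rule out a later choice.

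The rest is weaker. The sentence sits under the label Group comparison, so the natural test is the difference between solutions, taken once from one model. The plan nowhere suggests searching the times. Borrowing an SD from one time to size a repeated measures analysis is a common simplification and does not redefine the primary contrast. The ambiguity the text actually creates, 60 min or average, is worth 6-8% against 5%. The larger figures need an unrestricted search over six times and depend on an assumed correlation. The session's own pre-injection score is the obvious covariate. An unnamed period term matters little: including it moved simulated error at 60 min by at most 0.1 point when there was no period shift.

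**Conclusion.** The plan is under-specified here but not wrong, and no change follows. Carried out in the ordinary way, with one treatment effect from the stated repeated measures ANCOVA, it holds 5%. The inflation is conditional on a choice made after unblinding that the plan does not propose: about 6-8% between 60 min and the average (r = 0.9 to 0.5), and about 9-24% for the best of six times (r = 0.95 to 0.3).

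Choosing between 60 min and the average is a fair trade-off whose price depends on a time course the documents do not settle. Their only human evidence on duration, the Background report of over 5 hr at about 60 µg, covers the 4 hr window. If the effect at 100 µg is similarly sustained, the average has 85-97% power for 0.7, which is no worse than the plan claims.

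These figures assume 40 evaluable patients, a two-sided test, 1.5 as the SD of each paired difference (the plan gives it as the SD of a pain reduction), equal SDs at all six times, and correlations the documents do not state.

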## **STUDY DESIGN**

Inclusion Criteria: We request permission to study up to 44 subjects so that we will have 40 evaluable subjects.

1. Male or female  $\geq 18$  and  $< 70$  years of age, with a BMI  $< 40$ .
2. Presence of neuropathic pain for  $> 6$  months, with primary pain area below the umbilicus.

We will focus recruitment efforts on low back pain with a neuropathic component to the lower extremities, but will accept other causes of neuropathic pain.

3. Female subjects of child-bearing potential and those  $< 1$  year post-menopausal, must be practicing highly effective methods of birth control such as hormonal methods (e.g., combined oral, implantable, injectable, or transdermal contraceptives), double barrier methods (e.g., condoms, sponge, diaphragm, or vaginal ring plus spermicidal jellies or cream), or total abstinence from heterosexual intercourse for a minimum of 1 full cycle before study drug administration.

4. Blood pressure (systolic 90-150 mmHg; diastolic 50-90 mmHg) resting heart rate 45-100 beats per minute.

5. All subjects must be vaccinated against SARS-CoV-2, with proof via vaccination card or the NC HHS form.

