### **RANDOMIZATION GROUPS**

A computer generated randomization will be used to determine the group for each subject. Subjects will be randomized to receive an intrathecal injection of the saline placebo or 100 µg oxytocin on the first study visit, with the other on the second.

**Study Visit 1:** The participant will report to the CTSI Clinical Research Unit (CRU) at least 3 days prior to study visit 2. The participant will review and sign the Informed Consent. After informed consent is adequately obtained, a detailed medical history will be obtained from the participant, female participants will have blood drawn and sent to the laboratory to determine pregnancy status. Participants will be trained to estimate pain quantitatively using a 2 cm^2 peltier controlled thermode (TSA®) applied to an area of normal skin outside the area of ongoing pain. Typically, the participant is exposed to temperatures between 38 and 51 C using a random staircase method.

During this training period, the participant's blood pressure, heart rate, and peripheral oxyhemoglobin saturation will be recorded. A 12 Lead electrocardiogram (ECG) will also be performed.

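### Does the power statement fail because its 1.5 is described as the spread of a change after an injection, not of the oxytocin–placebo difference?

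*Combined protocol and SAP*

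**What the plan says.** The power analysis under STATISTICAL RATIONALE relies on the team's earlier published work, "in which the patient population has an ongoing pain level of" 4.3 ± 2.0 and "a reduction in pain 60 min after injection of" 0.9 ± 1.5. From these it states that "a group size of 40 will allow us to observe a difference between placebo and treatment of 0.7", with α = 0.05 and 80% power. It does not give the formula, the sidedness, the SD of the oxytocin–placebo difference or a correlation between sessions. The analysis is named in one sentence: "Pain will be compared using a repeated measures ANCOVA".

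The design is a two-period crossover. The Protocol's METHODS paragraph has patients "randomized into one of 2 groups of 20 subjects each" and says that at the second session "they will receive the other intrathecal study drug solution". RANDOMIZATION GROUPS repeats this: one solution is given "on the first study visit, with the other on the second". STUDY DESIGN sets the numbers: "We request permission to study up to 44 subjects so that we will have 40 evaluable subjects".

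**The concern.** In a crossover, the precision of the treatment comparison depends on how much the oxytocin–placebo difference varies from patient to patient. As worded, 1.5 is something else: the spread of a change after one injection. If both sessions have that SD, the SD of the difference is 1.5 × √(2(1 − ρ)), where ρ is the between-session correlation of the changes, and the plan gives no ρ. The power claim would then hold for some values of ρ and fail for others, although it is stated without conditions. The term group size adds some doubt, because METHODS uses groups for the two sequences of 20.

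This sentence is the only stated justification for 40 evaluable patients, each of whom is to have two spinal injections. If the sessions were uncorrelated, an unadjusted comparison at 60 minutes would have 53% power for 0.7, not 80%.

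**Working it through.** **Inputs.** From STATISTICAL RATIONALE: difference 0.7, spread of change 1.5, spread of pain 2.0, α = 0.05, power 0.80. From STUDY DESIGN: n = 40 evaluable. Assumed: ± denotes an SD, and the test is two-sided. Power is from the noncentral t distribution with noncentrality 0.7 × √40 / SD of the difference, on 39 df (38 with a period term; results barely differ).

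**1. The plan's own figure.** Take 1.5 as the SD of the paired difference. Noncentrality = 0.7 × 6.325 / 1.5 = 2.95. Power at 0.7 is 82%, the difference detectable with 80% power is 0.68, and 39 patients are needed. This agrees with 0.7 and 40. Other readings with an SD of 1.5 do not: a parallel design with 40 per arm gives 55% power, one with 20 per arm gives 31%, and uncorrelated sessions give 53%.

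**2. Largest SD that supports the claim.** Solving for 80% power at exactly 0.7 gives a maximum SD of the difference of 1.54. The plan prints one decimal, and 0.7 to one decimal covers detectable differences up to 0.75, which corresponds to an SD of about 1.65.

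**3. If 1.5 is a single-session SD, unadjusted at 60 minutes.** Minimum ρ = 1 − 1.540² / (2 × 1.5²) = 0.47. With the rounding allowance, it is 1 − 1.65² / (2 × 1.5²) = 0.40.

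| Assumed ρ | SD of difference | Power at 0.7 | Detectable at 80% power |
|---|---|---|---|
| 0 | 2.12 | 53% | 0.96 |
| 0.3 | 1.77 | 68% | 0.81 |
| 0.4 | 1.64 | 75% | 0.75 |
| 0.5 | 1.50 | 82% | 0.68 |
| 0.7 | 1.16 | 96% | 0.53 |

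**4. Baseline adjustment, as in an ANCOVA.** If pain has SD 2.0 both before and after injection, a change SD of 1.5 implies a baseline-to-60-minute correlation of 1 − 1.5² / (2 × 2.0²) = 0.719. The residual SD is 2.0 × √(1 − 0.719²) = 1.39, and the minimum ρ falls to 1 − 1.540² / (2 × 1.391²) = 0.39.

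**5. Baseline adjustment and all six post-injection times.** Assume a constant effect, the six times averaged, and correlation w between changes within a session. The variance of the mean change is 2.25 × (1 + 5w) / 6. The covariance of change with baseline is 4 × 0.71875 − 4 = −1.125, so adjustment removes 1.125² / 4 = 0.316.

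- w = 0.5: 1.3125 − 0.316 = 0.996, residual SD 1.00. At ρ = 0 the SD of the difference is 1.41, power at 0.7 is 86%, and the detectable difference is 0.64.
- w = 0.8: 1.875 − 0.316 = 1.559, residual SD 1.25. Minimum ρ = 1 − 1.540² / (2 × 1.559) = 0.24; at ρ = 0, power is 69%.

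In steps 4 and 5, ρ is the between-session correlation of the baseline-adjusted quantities. The values of ρ and w are assumptions; the documents give neither.

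**The case for a change.** The strongest case for a change is that the reading which reproduces 0.7 treats 1.5 as something the text does not call it. On the literal reading, the claim depends on a correlation that nobody has written down. Baseline adjustment and averaging reduce that dependence but need not remove it: at w = 0.8, some positive correlation is still required. The plan does not say which times or covariates enter the ANCOVA, so the favourable calculation in step 5 cannot be credited to it as fact. The earlier work is the team's own, so one look-up and an edited sentence would settle the matter.

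Most of this stands as description. The label is imprecise, the correlation is absent, and a reader cannot tell from the document what the 1.5 measures. It does not stand as a case that the number is wrong. The one look-up that could decide it is in a source outside the documents. Printing a list of detectable differences at assumed correlations, for an unadjusted 60-minute comparison, would replace one unexplained input with several unsourced ones, for an analysis the plan does not use. As for group size, METHODS and STUDY DESIGN together leave no real doubt that 40 is the number of evaluable patients, 20 per sequence.

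**Conclusion.** No change to the plan is needed. The stated 0.7 is reproduced (0.68, with 82% power at 0.7) by a paired calculation that matches the crossover and the 40 evaluable patients. If 1.5 is a single-session SD, the required between-session correlation is about 0.47 for an unadjusted comparison at 60 minutes and 0.39 with baseline adjustment. With adjustment and six times averaged, it is about 0.24 at w = 0.8, and none is needed at w = 0.5. A requirement of 0.47 is therefore too strict a test of the planned analysis.

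These results assume that ± is an SD, a two-sided test, equal SDs in both sessions and, for step 5, a constant effect over the six times. They do not prove that power is adequate; they show that the documents give no ground for calling it inadequate. What remains is a labelling gap. A statistician would read the 1.5 as the paired SD or check it against the team's earlier data, and clarifying it would leave enrolment, endpoint and analysis as they are.
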